Patient participants: Basic demographic data of age, sex, height and weight will be collected at baseline. Key baseline covariate factors to be collected at baseline are pain duration, pain location for the actual presenting MSKP complaint, number of other sites with MSKP, previous health care interventions for presenting MSKP complaint in the last 3 months, previous health care interventions for other MSKP sites in the last 3 months, number of comorbidities, analgesic medication use (type and consumption), level of education, employment and self-reported sick leave for the presenting MSKP complaint.

Physiotherapist participants: Basic demographic data of age, sex, department, level of education and number of years working as a physiotherapist will be collected prior to the start of patient recruitment.

Patient Reported Outcome Measures (PROMs)

For information on the time points for data collection of each PROM and PREM see patient participant timeline and Figure 4.

Primary outcome measures

Both primary outcome measures will be collected and analysed via group mean change from baseline. Primary outcome analysis time points are 1) Baseline to 24 hours post initial physiotherapy consultation and 2) Baseline to three months.

- Pain intensity

Pain intensity is chosen as a primary outcome for this study as it is a core outcome measure for intervention studies on pain (Chiarotto et al., 2018). Average pain intensity in the previous 24 hours will be measured using a numerical rating scale (NRS) (0-11 from 0 = no pain to 10 = worst imaginable pain) (Jensen et al., 1999). The average pain intensity NRS rating related to the past 24 hours has been chosen to reduce overlap of the ratings at the separate data collection time points. Consensus from the VIII International Forum on Primary Care Research on LBP and the median of study results from systematic reviews of pain intensity ratings in acute and chronic pain suggests that the minimal clinically important difference (MCID) for pain intensity is two points (Olsen et al., 2017; Olsen et al., 2018; Ostelo et al., 2008).

- Pain self-efficacy

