This protocol outlines the principal features of the statistical analysis for this study. A full statistical analysis plan (SAP) has been published on Clinicaltrials.gov alongside this protocol and prior to the completion of patient recruitment (September 25, 2024).

Participant characteristics

Patient: Group characteristics will be presented using descriptive statistics. Baseline analysis between the intervention and control groups will be conducted to ensure the comparability of the groups.

Physiotherapist participants: Group characteristics (age, sex, department, highest educational level, number of years of clinical experience, adherence to protocol) will be presented using descriptive statistics.

Analysis of primary outcomes

Magnitude of within and between-group change on primary outcomes from baseline to 24-72 hours prior to the initial physiotherapy consultation, 24 hours post initial physiotherapy consultation and three months post-baseline will be analysed through mixed models. Data will be compared based on the 'intention to treat' (ITT) principle. Sensitivity analyses applying per-protocol, complier average causal effect (CACE) analyses and analyses applying study specific MCID associated with dichotomised anchor response on the GRoC will be explored. Sensitivity analyses to adjust for all measured baseline covariates will also be performed to investigate the presence of equipoise as the result of randomisation (Thabane et al., 2013).

Multiplicity/ type I (a) error

The outcomes collected in the study are considered as separate entities and, therefore, restrictive multiplicity penalisation of the model is not required (Dmitrienko & D'Agostino 2013). Adjustment will be used for repeated measures over time for separate test conditions.

Analysis of secondary outcomes

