4. Three months post-baseline (primary time point two).

In addition, patients' reported experiences of the film and PROMs will be collected directly after exposure to the film in the intervention group. Secondary physiotherapist and patient reported experience measures (PREM) will be collected at time point 3. Healthcare register data relating to the three month study period for each participating patient will be collected after the completion of PROMs and PREMs data collection for all participants.

Data on the physiotherapists' adherence to the Pain-SMART strategy will be collected after all the first 450 included participants have had their first physiotherapy consultations (after time point three) approximately eight months after the inclusion of the first participant and prior to the start of patient inclusion to the qualitative phase of the trial. For primary and secondary PROM data the primary time points are defined as 24 hours post initial physiotherapy consultation (primary time point one) and three months post-baseline (primary time point two). The data collection is described in full in the trial protocol.

Outcome definitions

The primary and secondary outcomes are described in full in the trial protocol. Both trial arms have the following outcomes measured:

Primary outcomes

- Pain intensity

Self-reported average pain intensity in the previous 24 hours will be measured using numerical rating scales (NRS). Score range: 0-10 with 0 = no pain and 10 = worst imaginable pain.

- Time Frame: collected at baseline, 24 hours post initial physiotherapy consultation and at three months post-baseline.
- Calculation to derive outcome:
 - Between group mean change over time from baseline to 24 hours post initial physiotherapy consultation (primary time point one)
 - Between group mean change over time from baseline to three months post-baseline (primary time point two)

-Pain self-efficacy

Self-reported pain self-efficacy will be measured using the Pain Self-efficacy Questionnaire 10 (PSEQ-10). The PSEQ-10 is a 10-item questionnaire. Score range: 0-60, a higher score indicating greater pain self-efficacy.

- Time Frame: collected at baseline, 24 hours post initial physiotherapy consultation and at three months post-baseline.

- Calculation to derive outcome:
 - Between group mean change over time from baseline to 24 hours post initial physiotherapy consultation (primary time point one)

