An internal pilot interim analysis was planned and conducted after 50% of the sample had reported outcomes at time point 2 (pre physiotherapy consultation) and 3 (primary time point one, post initial physiotherapy consultation). This to evaluate the viability of the a-priori sample size calculation and the recruitment frequency. The analysis utilised linear mixed models to investigate between group difference (effect size) for change from baseline to time points 2 and 3 in outcome. The significance level for the interim analysis was $p=0.05$. After interim sample size calculation, the sample size was slightly adjusted when taking loss to follow-up into account. The sample size calculation is described in the trial protocol. The trial would have been stopped if the internal pilot interim analysis could not be performed due to not attaining 50% of the sample size at Time point 2 and 3 within 6 months. No further interim analyses are planned.

Final analysis

The trial is planned to finish recruitment of new patient participants in Dec 2024 – Jan 2025. The final three-month follow-up data collection will therefore be in Mar - Apr 2025. All outcomes will be analysed collectively.

Analysis methods

Primary outcome analysis

-Pain intensity and Pain self-efficacy

Hypothesis testing for the two primary outcomes *pain intensity* and *pain self-efficacy* (score on average pain NRS in the last 24 hours and PSEQ-10) will be based on analysis of group mean change from baseline. Baseline scores and group mean change in primary outcome scores from baseline to primary time points one and two for the intervention and control groups and the between-group change for these time points will be presented as means and CI. The within and between-group change on primary outcomes from baseline to 24 hours post initial physiotherapy consultation and three months post-baseline will be analysed according to ITT principles using a maximum likelihood approach for mixed models adjusted for a relevant covariance structure. The models will be adjusted for baseline covariates where relevant. Baseline factors that will be analysed for potential covariate adjustment include: age, sex, educational level, employment, pain duration, number of pain sites, comorbidities, days to initial physiotherapy consultation, previous healthcare interventions, ÖMPSQ risk category, self-reported sick leave and analgesic medication consumption.

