Patients receive seven questions and physiotherapists 3 questions regarding their experience of the initial physiotherapy consultation. Between group mean difference for responses to these questions will be analysed using independent sample t-tests. These analyses will be presented as mean and SD for each group and the between group difference in mean and CI. Three of the patient questions will be analysed for concordance with the matched physiotherapists' questions. Concordance within the intervention group and control group will primarily be analyzed by calculating intraclass correlation coefficient (ICC) with 95% confidence interval on each question as well as all three questions combined. Two-way random effects model will be used for ICC, assuming raters to be randomly selected. The ratings are single measures analyzed for consistency, to measure systematic differences between ratings. Patients and physiotherapists are treated as two independent raters, rating each of the three questions.

Sensitivity analyses

The following are all re-analyses of the primary and secondary outcomes under different conditions:

- Per-protocol analysis
- Complier average causal effect (CACE) analysis
- Responder analysis
- Complete case analysis (in case of >5% missing data)

Per-protocol analysis

Per-protocol analyses for the primary and secondary outcomes will be conducted to assess robustness of the ITT analyses and to further inform decisions regarding superiority. The sample of the patients for the per-protocol analyses will be as follows:

- Intervention group: patients receiving the PainSMART-strategy with no or minor deviation from protocol.
- Control group: patients receiving intervention with no or minor deviation from protocol.

Data on the physiotherapists' self-reported adherence to the protocol will be cross-referenced with the intervention respective control group patient consultations that each physiotherapist has conducted. This, in combination with the intervention group patients' self-reported exposure to the film, will provide data on deviation from protocol.

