Baseline factors that will be analysed for potential covariate adjustment include: age, sex, educational level, employment, pain duration, number of pain sites, comorbidities, days to initial physiotherapy consultation, previous health care interventions, ÖMPSQ risk category, self-reported sick leave and analgesic medication consumption. Between-group differences on outcomes from baseline to 24-72 hours prior to the initial physiotherapy consultation, 24 hours post the initial physiotherapy consultation and three months post-baseline will be analysed.

Complier average causal effect (CACE) analysis

CACE estimation will be implemented in a structural equation modeling program (eg Mplus) using a maximum likelihood approach. As displayed in the following Directed Acyclic Graph (DAG) model (Figure 1), the covariate (X = baseline score for observed outcome variable) predicting both the outcome (Y = Follow-up score of observed outcome variable) and compliance status (C = dichotomous adherence latent class variable).

[figure not shown]

Figure 1. Directed Acyclic Graph (DAG) for CACE analysis

Solid lines from the square boxes for observed variables indicate regressions among these variables. For example, the path from Z (a binary treatment variable) to Y (the outcome) illustrates the treatment effect. The dashed lines originating from the latent class variable C to the regression of observed variables (Z, X) on the outcome suggest that the effects on the outcome can differ across compliance classes. The solid line from the latent class variable to the outcome shows that the means for noncompliers and compliers can differ. The model will be adjusted for other baseline covariates where relevant. Baseline factors that will be analysed for potential covariate adjustment include: age, sex, educational level, employment, pain duration, number of pain sites, comorbidities, days to initial physiotherapy consultation, previous health care interventions, ÖMPSQ risk category, self-reported sick leave and analgesic medication consumption. Between-group differences on outcomes from baseline to 24-72 hours prior to the initial physiotherapy consultation, 24 hours post initial physiotherapy consultation and three months post-baseline will be analysed (Hesser, 2020).

Responder analysis

Responder analyses for the primary and secondary outcomes will be based on calculation of the trial specific MCIDs. The sample of the patients for the responder analyses will be as follows:

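### The primary test is based on change from baseline and the SAP does not say how the baseline score enters the mixed model; pre-specifying it as a covariate is a free gain in precision and protection against chance imbalance

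*SAP*

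**What the plan says.** The Protocol (Primary outcome measures) says: "Both primary outcome measures will be collected and analysed via group mean change from baseline". The SAP (Outcome definitions) derives each primary outcome accordingly, for example "Between group mean change over time from baseline to three months post-baseline (primary time point two". Under Primary outcome analysis the SAP repeats the basis of the test ("score on average pain NRS in the last 24 hours and PSEQ-10) will be based on analysis of group mean change from baseline") and specifies an intention-to-treat mixed model fitted by maximum likelihood.

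On covariates, the same section says: "The models will be adjusted for baseline covariates where relevant". It then names 12 candidates: age, sex, education, employment and pain duration, then "number of pain sites, comorbidities, days to initial physiotherapy consultation, previous healthcare interventions, ÖMPSQ risk category", and finally self-reported sick leave and analgesic consumption. The baseline value of the outcome is not named, but the list is introduced with the word *include* and so may be open.

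Elsewhere the baseline score is treated explicitly. The CACE section has "the covariate (X = baseline score for observed outcome variable) predicting both the outcome", and the mediation models adjust for the baseline score of the outcome.

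Two other places bear on the point. The SAP (Demography and baseline characteristics) plans significance tests to screen the arms for baseline imbalance and lists the baseline PROM scores in that section. The Protocol (Analysis of primary outcomes) promises: "Sensitivity analyses to adjust for all measured baseline covariates will also be performed to investigate the presence of equipoise as the result of randomisation". The SAP's own list of sensitivity analyses, introduced by "The following are all re-analyses of the primary and secondary outcomes under different conditions", has four entries, and this is not one of them.

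**The concern.** Three different models fit the SAP's text: baseline as a repeated response with separate arm means, baseline as a covariate, or baseline as a response with a common mean across arms. The first has the precision of a simple change score. The other two are more precise whenever the baseline/follow-up correlation is below 1 (with equal variances), and they do not carry a chance baseline difference into the estimate. Allocation is by simple randomisation (Protocol, Allocation and sequence generation), which does not limit such differences.

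The imbalance screen does not settle the matter, because no section says what follows a flagged result. If a flag is what makes a covariate relevant, the primary model would be chosen after looking at the data, which is inferior to adjustment fixed in advance. What is at stake is the width of the primary intervals and the credibility of the result in a trial whose arms happen to start unequal.

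**Working it through.** **Inputs.**
- n = 204 per arm: 408/2, from the Protocol's Sample size section.
- Planning SDs in the same section: 4 for the NRS and 23.20 for the PSEQ-10. The Protocol does not say whether these are SDs of scores or of change.
- Assumptions: correlation r between baseline and follow-up of 0.2, 0.5 or 0.8 (none is given); equal SD at both visits; score SD from 2 to 4 (NRS) and 12 to 23.2 (PSEQ-10).

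The plan gives no precision figure for this choice, so there is none to reproduce.

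**Step 1: precision.** In units of (2/n)·SD², the variance of the arm difference is 2(1−r) for a change score and 1−r² after conditioning on baseline. The ratio is (1+r)/2, and the interval narrows by 1−√((1+r)/2).

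| r | Variance ratio | Narrower by |
|---|---|---|
| 0.2 | 0.60 | 22.5% |
| 0.5 | 0.75 | 13.4% |
| 0.8 | 0.90 | 5.1% |

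**Step 2: in points.** The 95% half-width is 1.96·SD·√(2/204)·√(2(1−r)) for change and 1.96·SD·√(2/204)·√(1−r²) after conditioning.

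| r | NRS, SD 2 | NRS, SD 4 | PSEQ-10, SD 12 | PSEQ-10, SD 23.2 |
|---|---|---|---|---|
| 0.2 | 0.49 to 0.38 | 0.98 to 0.76 | 2.95 to 2.28 | 5.70 to 4.41 |
| 0.5 | 0.39 to 0.34 | 0.78 to 0.67 | 2.33 to 2.02 | 4.50 to 3.90 |
| 0.8 | 0.25 to 0.23 | 0.49 to 0.47 | 1.47 to 1.40 | 2.85 to 2.70 |

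At r = 0.5 the gain is about 0.05–0.10 NRS points and 0.3–0.6 PSEQ-10 points. There the two readings of the planning SDs agree, because 2(1−r) = 1. At r = 0.2 they do not: with 4 read as the SD of change, the NRS half-width goes from 0.776 to 0.601, a gain of about 0.17 instead of 0.22.

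**Step 3: does a mixed model avoid this by itself?** No. In simulation with complete data and 204 per arm, a mixed model with baseline as a response and free arm means returned the change-score difference to within about 3e-14. Adjusting for baseline gave standard-error ratios of 0.800, 0.871 and 0.923 at r = 0.3, 0.5 and 0.7, against 0.806, 0.866 and 0.922 from theory.

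**Step 4: chance imbalance.** The baseline difference has SE √(2/204) = 0.099 SD, so 1.96 SE is 0.194 SD. The intervention arm starts at least that much worse in 2.5% of trials. Given a baseline difference D, the change-score estimate shifts by (1−r)D, with SD √((2/n)(1−r²)). The SAP (Confidence intervals and P values) sets one-sided 0.05 and applies Bonferroni over repeated time points; with two primary time points that gives 0.05/2 = 0.025. At D = 0.194 SD and r = 0.5, the shift is 0.097, the critical value is 1.96 × 0.099 = 0.194, and the conditional SD is 0.099 × √0.75 = 0.086. Then z = (0.194 − 0.097)/0.086 = 1.13 and the error is 13%. The same steps give 18% at r = 0.2 and 8% at r = 0.8.

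**Step 5: what is not at risk.** In 2,000 simulated trials per setting, the overall one-sided 5% error was 0.040–0.054 both with free baseline means and with baseline means constrained equal. Power of the change-score test for d = 0.5 at one-sided 5% is lowest at r = 0.2: 0.5/(0.099·√1.6) = 3.99, less 1.645, giving 0.9905. At one-sided 2.5% the same case gives 3.99 − 1.96 = 2.03, about 0.979.

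**The case against.** The strongest reply is that this is only a clarification. The covariate list is open, the authors condition on baseline in two other analyses, and they may well intend it here. If so, the estimate does not change. This stands, and the figures above apply only if baseline is not otherwise conditioned on.

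Second, the SAP does screen for imbalance. At a conventional 5% level (the SAP states none for the screen), a difference of 1.96 SE is exactly where it would flag. That is fair, so chance imbalance cannot be called ignored. But no consequence is specified, and smaller differences pass unflagged. Among simulated trials where the intervention arm started more than 1 SE worse, the one-sided 5% error with free baseline means was 0.20, 0.15 and 0.09 for r = 0.2, 0.5 and 0.8.

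Third, the Protocol's all-covariate sensitivity analysis would probably bring the baseline score in, and the SAP's silence does not withdraw it. This also stands, but it leaves the primary estimate unspecified.

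Fourth, the gain is modest against the two-point NRS MCID and the 5.5–8.5 PSEQ-10 range that the Protocol cites. It would be smaller still if ÖMPSQ category or other listed covariates already carry baseline severity. Both points are correct.

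A reader might go further and infer that the plan rejects baseline adjustment, that type I error is inflated overall, or that the trial loses its power. The documents and the arithmetic support none of these.

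**Conclusion.** The point holds as a gap in the primary model that can be closed with a better, costless specification. If the baseline score is not already conditioned on, adding it narrows the 95% intervals by about 22.5%, 13% or 5% at assumed correlations of 0.2, 0.5 or 0.8, and by less where other covariates overlap with baseline severity. It also removes a bias that, at the edge of the 2.5% of trials with the worst unfavourable starting imbalance, raises a one-sided 2.5% error to about 18%, 13% or 8%. Imbalance in the other direction lowers the error, and the average is nominal. Power for d = 0.5 at one-sided 5% is at least 99% either way.

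Defining the outcome as change from baseline is not itself a fault. Once baseline is in the model, the arm difference in change equals the arm difference in follow-up score.

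**What to change.** In the SAP, Primary outcome analysis, state that the mixed model for each primary outcome includes that outcome's baseline score and its interaction with time as pre-specified covariates, regardless of any imbalance test, with the primary contrasts at time points 3 and 4. Keep the unadjusted change-score estimate as a sensitivity analysis. Add to the SAP's sensitivity list the all-covariate analysis that the Protocol promises, so that the two documents agree. The outcome definitions in the Protocol (Primary outcome measures) and SAP (Outcome definitions) can stay as they are.

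Conditioning is sound here. Patients are randomised before baseline, but the Protocol (Blinding) gives both arms identical material until baseline data are complete, so the film cannot have affected the baseline score.

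The cost is a few sentences and no new data. Because the interim analysis of 29 February 2024 already estimated between-group effects with mixed models, the amendment should be dated and justified as made after that analysis and before the final unblinded one.
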